The use of local anesthetics always bodes a potential risk of local anesthetic systemic toxicity (LAST) as a result of systemic uptake from intravascular injection, rapid vascular absorption, or overdose of local anesthetic solution. We employ a multifaceted approach to minimize the risk of LAST by including local concentration and dose in the context of the patient’s weight during the regional timeout procedure, using epinephrine as both an intravascular marker and local vasoconstrictor to limit systemic uptake of local staying below the recommended upper limit of local anesthetic dose of 3mg/kg for bupivacaine with epinephrine, and aspirating frequently, including before any injection of local anesthetic solution, and in between each aliquot of 5cc of local before proceeding with dosing. This study has an exclusion criterion such that minimum body weight must be above 50kg for inclusion, so that no patients in whom the prescribed local anesthetic dose would be higher than the recommended upper limit of bupivacaine dosing will be enrolled, as detailed below.

Methods/Measurements

Design

This will be a randomized, triple-blinded, prospective, feasibility trial that will take place after approval from our Institutional Review Board. Investigational New Drug Exemption has been obtained from the US Food and Drug Administration for use of the perineural adjuvants and is filed as FDA IND Exemption 165506. Written informed consent will be obtained from all study participants prior to randomization. This trial has been registered on www.clinicaltrials.gov as NCT05676814.

Selection Criteria

Inclusion: Adults between 18 and 90 years of age undergoing cardiac surgery involving sternotomy at Atrium Health Wake Forest Baptist, and who have consented to participate and lack any contraindications to PIFB for postoperative analgesia will be recruited for participation in the study.

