Exclusion: Patients with any contraindications to regional anesthesia, such as history of allergy to amide local anesthetics or any of the perineural adjuvants; existing neurologic deficit in the chest wall; remaining intubated at the six hour point after block placement; weight under 50kg; undergoing emergency surgical procedures or urgent return to the operating room; active endocarditis or mediastinitis; moderate to severe right ventricular function before or after cardiopulmonary bypass; reliance on mechanical circulatory support devices, such as intra-aortic balloon pump or Impella; reliance on extracorporeal membrane oxygenation; localized or systemic infection; chronic use of high dose opioid analgesics (defined as daily use greater than 30 oral morphine milligram equivalents (OMME) for over one month prior to surgery); as well as those who are pregnant, will be excluded from participation. Intraoperative opioids will be limited to fentanyl, therefore patients who receive any other opioids will be excluded. Additionally, any administration of ketamine, methadone, and dexmedetomidine during intraoperative and postoperative settings will exclude the subjects from the study. Furthermore, postoperative administration of tramadol, NSAIDs, muscle relaxants, and Haldol will exclude the subjects from the study. Any patients who refuse enrollment or withdraw their consent will also be excluded and any of their information already collected will be destroyed.

Setting

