Subjects will be randomized on the day of surgery, specifically prior to the start of their procedure. Surgery will proceed as scheduled, and patients will be anesthetized and monitored per our usual cardiac anesthesiology practice with general anesthesia. At the end of the cardiopulmonary bypass circuit run, patients will be reassessed for the aforementioned exclusion criteria before the randomized block is placed. Patients will be blinded to their treatment arm assignment, as will all research personnel who be responsible for collection of outcome data, as well as the surgeons performing the cardiac procedure, and the critical care staff caring for the patients in the postoperative period. PIFB will be performed after skin closure and before transport from the operating room to the CVICU. For patients who are randomized at enrollment but later excluded due to exclusion criteria prior to block placement, their randomization assignment will be replaced at the end of the initial recruitment.

Interventions

Once the surgical team is finished with skin closure, bilateral PIFB will be placed by a faculty anesthesiologist well-versed in the performance of ultrasound-guided regional anesthesia and performance of PIFB blocks, or by a trained anesthesia resident or fellow directly supervised by them. This will be done by obtaining a longitudinal, parasagittal view of the costal cartilage 1-2cm lateral to the sternum at the level of the fourth or fifth rib and guiding a block needle in the cephalad direction in plane to the fascial plane between Pectus Major and Internal Intercostal muscles, with the goal of obtaining cephalad spread along the plane over multiple costal cartilage levels, as described previously²³. PIFB will be performed bilaterally using a volume of 30cc of local anesthetic solution per side, with dosing in 5cc aliquots only after confirming aspiration is negative for blood and that a small aliquot of local solution demonstrates spread in the intended plane. We will repeat aspirations in between each aliquot of 5cc of local anesthetic, as is our standard practice, to monitor for intravascular needle position.

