We define a minimum clinically important difference (MCID) to be a 10% reduction in area under the curve for our primary outcome. Given that no current data exist on the anticipated duration of PIFB with perineural adjuvants at our institution, we have decided to recruit 10 patients per arm for a total of 20 patients in this feasibility trial. Based on prior studies involving the use of perineural adjuvants with long-acting local anesthetics, we have noted an average duration around 20 hours for peripheral blocks performed at other sites with bupivacaine containing perineural adjuvants epinephrine, clonidine, and dexamethasone. We have therefore chosen 24 hours as the final time point, with serial checks starting at 6 hours post block placement to represent clinically important pain trajectories for patients recovering from cardiac surgery with sternotomy.

Data Analysis

Demographic information will be collected as mentioned above and compared between the groups to verify that randomization balanced important baseline variables between the control and experimental groups. For the primary outcome of AUC pain scores with use of incentive spirometry for the first 24 hours post block placement, we will compare mean and standard deviations of the overall integrated area under the curve using the trapezoid rule. For secondary outcomes with continuous variables, such as intubation or ICU duration, t-tests and confidence intervals will be calculated. For continuous variables with serial measurements, repeated measure analysis of variance (RMANOVA) will be used. Further assistance with statistical analysis is being elicited from the Clinical and Translational Science Institute (CTSI), and this IRB protocol will be updated with further details after final review with a statistician.

Missing Data Points

Missing data points for the primary outcome will be imputed by a mixed effects modeling framework that allows us to use all available data points to tests hypotheses about differences between the two groups at each time point. Models will be implanted using the 'lme4' package in R statistical software.

Human Subjects Protection

Subject Recruitment Methods

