Confidentiality will be protected by collecting only the requisite information required to assess the study outcomes, minimizing the collection of any information that could directly identify subjects. Each patient will be assigned a unique study identifier that will appear on the data collection form, and any protected health information that may directly identify the patient corresponding to the unique study identifier will be kept secure with access limited to designated study personnel. Following collection of all data, subject identifying information will be destroyed at the earliest opportunity, consistent with data validation and study design, producing an anonymous data set for analysis. All patient information collected will be kept confidential during recruitment as well as the remainder of the study. All identifying protected health information will be de-identified in the electronic database during data collection, which will be encrypted and secured in the Atrium Health Wake Forest Baptist private servers and only accessible by two-factor authenticated, password-protected computers. Only selected research personnel who are specifically enrolling patients or collecting or analyzing data will have access to the dataset. No reference to any individual participant will appear in reports, presentations, or publications that may arise from this study.

Data and Safety Monitoring

The principal investigators will be responsible for overall monitoring of the data and safety of study participants and will be assisted by other members of the research personnel in the identification of any safety concerns.

Reporting of Unanticipated Problems, Adverse Events, or Deviations

Each participating attending anesthesiologist will report to the principal investigators about any protocol violations, unanticipated problems with the protocol, or adverse events, which will promptly be reported to the IRB and corresponding government agency, if appropriate.

Resources/Citations

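### Destroying everything collected from anyone who withdraws consent removes randomised and treated patients from arms of 10, with no exception for allocation, safety or outcome data

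*Combined protocol and SAP*

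**What the plan says.** The rule is the last sentence of the exclusion paragraph under Selection Criteria: "Any patients who refuse enrollment or withdraw their consent will also be excluded and any of their information already collected will be destroyed". It sets no time limit and names no kind of record that is spared.

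Other sections fix whom it can reach:

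- Design: "Written informed consent will be obtained from all study participants prior to randomization".
- Randomization: "Subjects will be randomized on the day of surgery, specifically prior to the start of their procedure". Replacement is described only for patients "later excluded due to exclusion criteria prior to block placement, their randomization assignment will be replaced at the end of the initial recruitment".
- Measurements: pain and spirometry are recorded at 6, 12, 18 and 24 hours, followed by a telephone call at 30 days.

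Two sections depend on the data that the rule removes:

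- Missing Data Points: gaps in the primary outcome are to be handled by "a mixed effects modeling framework that allows us to use all available data points".
- Reporting of Unanticipated Problems, Adverse Events, or Deviations: attending anesthesiologists tell the principal investigators of protocol violations, "unanticipated problems with the protocol, or adverse events, which will promptly be reported to the IRB and corresponding government agency", if appropriate.

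On size, Power Analysis says "we have decided to recruit 10 patients per arm for a total of 20 patients in this feasibility trial" and sets the "minimum clinically important difference (MCID) to be a 10% reduction in area under the curve for our primary outcome". No section defines an analysis population or asks for withdrawals to be reported by arm.

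**The concern.** Withdrawal of consent after randomisation is a post-randomisation event. Deleting those patients breaks the comparison of the groups as randomised, and it does so by a written rule, not by accident. If withdrawal is related to pain, the arm that loses its patients in most pain looks better than it was. Such a link is plausible when the primary measure is pain on deep breathing after sternotomy, but the documents do not show it.

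Two features make this matter more here. The arms have 10 patients each, so one deletion is visible in the mean. And the trial is described as a feasibility study, for which the number, timing and arm of withdrawals are among the most useful results; nothing protects that record. On safety, Risks to Subjects names pneumothorax and local anesthetic systemic toxicity as potential risks, so the study's own record of events in treated patients should not depend on whether consent was later withdrawn.

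**Working it through.** **Step 1. Whom the rule reaches.** The order of events is consent, randomisation before the procedure, block after skin closure, four assessments to 24 hours, then the 30-day call. Consent can be withdrawn at any point after it is given.

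- Exclusion before the block under the exclusion criteria: the assignment is replaced (Randomization).
- Withdrawal after the block and before 24 hours: partial pain scores are destroyed, and no replacement is described.
- Withdrawal after 24 hours and before the 30-day call: a complete primary outcome is destroyed, and no replacement is described.

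**Step 2. The plan's own figure.** 10 per arm × 2 = 20, as stated. The documents give no significance level, power, SD or dropout rate, so nothing more can be reproduced. One patient is 1/10 = 10% of an arm and 1/20 = 5% of the trial.

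**Step 3. Shift from one deletion.** Let M be the mean AUC of all 10 patients in an arm, and let the deleted patient lie d above M. The mean of the other nine is (10M − M − d)/9 = M − d/9.

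Worst-case illustration, d = 2 SD: the shift is 2/9 = 0.222 SD. The coefficient of variation (CV) of the AUC is not given; 30% to 60% is assumed.

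- CV 30%: 0.222 × 30% = 6.7% of the mean.
- CV 60%: 0.222 × 60% = 13.3% of the mean.

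These are 67% and 133% of the 10% minimum important difference.

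**Step 4. Less extreme patients.** With d as a percentage of the arm mean, the shift is d/9:

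| Deleted patient's AUC above arm mean | Fall in arm mean |
|---|---|
| 25% | 2.8% |
| 50% | 5.6% |
| 90% | 10.0% |

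The expected maximum of 10 normal values is about 1.54 SD above the mean. For that patient the shift is 1.54/9 = 0.171 SD, or 5.1% to 10.3% at the same CVs.

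**Step 5. Set against sampling error.** The standard error of the difference between arms is √(1/10 + 1/10) = 0.447 SD, or 13.4% to 26.8% of the mean at CV 30% to 60%. The worst-case shift is 0.222/0.447, about half of one standard error.

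**Step 6. Chance that it happens.** The withdrawal rate w is not given. The chance of at least one withdrawal among 20 is 1 − (1 − w)^20: 33% at w = 2%, 64% at 5% and 88% at 10%.

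**Step 7. Power.** At an assumed two-sided 5% level and CV 30%, power for a 10% difference is 11.2% with 10 per arm and 10.5% with 9 per arm. The loss of power is minor; bias and lost records are the issue.

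**The case against.** Several stronger readings are tempting, and the documents do not support them.

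- **A patient who refuses further spirometry is deleted.** A reader might infer this, but the rule applies to withdrawal of consent. Declining an assessment leaves a missing value, which the Missing Data Points section covers. This objection stands, and it removes much of the route by which painful testing would lead to deletion. The protocol never separates the two events, so the line should be drawn in writing.
- **Patients vanish without trace.** The text does not say that the randomisation list or a count of withdrawals is erased, or that the hospital record is touched. It is equally true that nothing requires the list or the count to be kept.
- **The rule contradicts the missing-data and adverse-event sections.** It does not. Destroyed data are no longer available, so the mixed-model sentence can still be followed. An event can be reported before a patient withdraws, and nothing recalls a filed report. What remains is that partial data a mixed model could use are lost, the study data behind a report may go, and information not yet reported may be lost.
- **The shift is as large as the minimum important difference.** Only under extreme assumptions. A patient 2 SD above the mean is beyond the expected worst of 10. At CV 60% that patient's AUC is 1 + 2 × 0.60 = 2.2 times the arm mean, which on a 0 to 10 scale needs an arm mean of about 10/2.2 = 4.5 or less.

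It can also be said that destruction on withdrawal is a promise made to protect participants. The consent form is not among the documents, so what participants were told cannot be checked. This limits how absolute any retention rule can be. It does not make blanket destruction necessary, because Confidentiality and Privacy already provides for coded, de-identified data.

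**Conclusion.** The concern holds as a harmful stated rule. As written, a randomised and treated patient who withdraws consent is removed from the analysis together with allocation, safety and outcome data, even after a complete 24-hour primary outcome. The rule undermines the use of partial data and the study record behind adverse-event reports; it does not contradict either section.

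The certain part of the size is 10% of an arm per patient. The 6.7% to 13.3% shift is a worst case that rests on an assumed CV of 30% to 60% and a patient 2 SD above the mean. For patients 25% to 50% above the mean the shift is 2.8% to 5.6%. The direction favours an arm only if those who withdraw from it have more pain than the rest, which is plausible but undocumented.

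The remedy keeps only what was collected before withdrawal. It recovers the whole primary outcome for someone who leaves after 24 hours, and part of it for someone who leaves earlier. For people who refuse enrolment, destruction causes no analysis problem.

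**What to change.** Replace the sentence, for enrolled patients, with wording to this effect:

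- Withdrawal of consent stops further collection.
- Data collected up to withdrawal are kept and analysed in the assigned arm unless the participant asks for their removal.
- The assigned arm, the time of withdrawal and any adverse events are kept as the consent form and the IRB allow.
- Declining a single assessment is a missing data point and not a withdrawal of consent.
- Withdrawals are reported by arm.

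Destruction may stay for people who refuse enrolment. Anyone already consented under the current wording should have it honoured.

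The planned total of 20 does not change. The cost is a protocol and consent amendment through the IRB, and the default for participants moves from destruction to retention. Data Analysis already foresees an update after review with a statistician, so the change can go in with it.

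### Assignments lost before the block are replaced only at the end of recruitment; with 10 per arm fixed, this implies that the last patients fill arms set by earlier exclusions, which anyone knowing the vacated arms could predict.

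*Combined protocol and SAP*

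**What the plan says.** The Randomization section sets the order of events. On timing: "Subjects will be randomized on the day of surgery, specifically prior to the start of their procedure". At the end of the bypass run, "patients will be reassessed for the aforementioned exclusion criteria before the randomized block is placed". The block follows skin closure. An arm has therefore been issued before the recheck that may remove the patient.

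Some exclusion criteria under Selection Criteria can only be settled during or after the operation, for example "moderate to severe right ventricular function before or after cardiopulmonary bypass", or the intraoperative use of certain drugs. Losses between randomization and block are therefore foreseen.

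The rule for those losses begins "For patients who are randomized at enrollment but later excluded due to exclusion criteria prior to block placement" and ends "their randomization assignment will be replaced at the end of the initial recruitment". It does not say whether the replacement gets the same arm or a new draw, in what order replacements are issued, or who handles them. Its opening words also place randomization at enrollment, which does not match the day-of-surgery timing earlier in the same paragraph.

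Under Power Analysis, "we have decided to recruit 10 patients per arm for a total of 20 patients".

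On masking: "Patients will be blinded to their treatment arm assignment, as will all research personnel who be responsible for collection of outcome data". Surgeons and critical care staff are added to that list. The anesthesiologist who places the block and the person who prepares the solution are not named. No sequence generation, block size, list holder or concealment method is described.

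**The concern.** What is replaced is the assignment, and the target is exactly 10 per arm. Independent new draws would not guarantee that total; refilling the vacated arms would. On that reading, a late patient's arm follows from an earlier exclusion and not from a new concealed draw.

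The vacated arm was issued before the exclusion, so someone in the operating room may know it. The anesthesia team is absent from the blinded list, and would ordinarily be placed to judge some of the criteria at the recheck. Excluding a patient could then return a known arm, to be filled by a patient not yet chosen.

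Two things would be at stake. Choice of whom to approach late in the trial could be influenced by knowledge of the arm that is waiting, and masked outcome assessment does not protect against that. Refilled patients also all come last, so if the vacancies fell in one arm, those late patients would all be in that arm. With 10 per arm, each refill is 10% of its arm.

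**Working it through.** **Inputs from the documents.** 10 per arm, and 10 + 10 = 20, which agrees with the stated total. No exclusion rate, standard deviation or power figure is given, so there is no other plan figure to reproduce.

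**Assumptions.** *k* pre-block exclusions, *k* = 1 to 5 (k/20 = 5% to 25% of the 20 patients). Exclusions are unrelated to arm, so the number *a* of vacancies in one arm is hypergeometric from a 10:10 list. The vacated arms are refilled. The observer knows which arms were vacated.

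**Formulas.**
- P(a) = C(10,a) × C(10,k−a) / C(20,k).
- Vacancy order kept: every refill is known, 100%.
- Shuffled, arms not learned as they are issued: always guess the majority arm; the share correct is max(a, k−a)/k.
- Shuffled, each arm learned after issue: guess the arm with more places left. With a and b places left, the expected number correct is g(a,b) = max(a,b)/(a+b) + [a/(a+b)] g(a−1,b) + [b/(a+b)] g(a,b−1), with g(0,0) = 0. The share is g/k.

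**Worked case, k = 2.** P(both in one arm) = 2 × 45/190 = 0.474, and P(one in each) = 100/190 = 0.526.
- Arms learned: a split pair gives (0.5 + 1)/2 = 0.75, so 0.474 × 1 + 0.526 × 0.75 = 0.868.
- Arms not learned: 0.474 × 1 + 0.526 × 0.5 = 0.737.

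**Worked case, k = 3.** P(all in one arm) = 2 × 120/1140 = 0.211, and P(2:1 split) = 0.789. For a 2:1 split, g = 2/3 + (2/3)(1.5) + (1/3)(2) = 2.333, a share of 0.778.
- Arms learned: 0.211 + 0.789 × 0.778 = 0.825.
- Arms not learned: 0.211 + 0.789 × 0.667 = 0.737.

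**Expected share of refills guessed correctly**

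| k | Vacancy order kept | Shuffled, arms learned | Shuffled, arms not learned | All vacancies in one arm |
|---|---|---|---|---|
| 1 | 100% | 100% | 100% | 100% |
| 2 | 100% | 87% | 74% | 47% |
| 3 | 100% | 82.5% | 74% | 21% |
| 4 | 100% | 79% | 67% | 9% |
| 5 | 100% | 76% | 67% | 3% |

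**Price of giving up exact balance.** The variance of the difference relative to 10 v 10 is (1/n₁ + 1/n₂)/(1/10 + 1/10).
- 11 v 9: 0.2020/0.2 = 1.010, or +1.0%.
- 12 v 8: 0.2083/0.2 = 1.042, or +4.2%.

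**The case against.** The best reply is that the protocol never says the same arm is re-issued. A new draw fits the wording, and then the late arms do not follow from the vacancies. That stands as a caveat: re-issue is an inference from the fixed 10 per arm. But the protocol does not state a new draw either.

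A second reply is that nobody who recruits is shown to know an arm. Research staff approach patients, the staff who collect outcomes are masked, and the trial is described as triple-blinded. The documents do not say who prepares the solution, who does the recheck, or whether the block operator is unmasked. This also stands. A reader might infer that selection bias has entered, or will enter, the primary comparison. The text supports only that nothing in it rules this out.

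A reader might also set the guess rates against one half. That is not the right comparator for a practical list. In a check with assumed randomly varying block sizes (2 and 4; 2, 4 and 6; or 4 and 6), an observer who knows all past arms and the possible sizes still guesses about 68% to 72% correctly. The remedy therefore works by keeping arms concealed and by not returning a known arm for later use. It does not make a fully informed observer powerless.

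A reader might go on to turn the guess rates into a shift in the primary AUC. The documents give no exclusion rate, no expected pain score and no prognostic difference, so any such figure would rest on assumed inputs alone.

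The calendar-time point is weak. Vacancies all in one arm become unlikely beyond two or three, and the documents show no time trend. Finally, this is a 20-patient feasibility trial whose size is not power-based, and the number of refills may be zero. That limits the importance of the point. It does not remove it, because the Objectives state a comparative hypothesis on the primary AUC and the correction is cheap.

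**Conclusion.** The point holds in conditional form. The stated rule defers replacement to the end of recruitment and, with 10 per arm fixed, implies that the last patients fill arms set by earlier exclusions. If so, someone who knows the vacated arms predicts all refills when vacancy order is kept or when there is one vacancy. In shuffled order with two to five vacancies, that person predicts 87% to 76% if each arm is learned after issue, and 74% to 67% if not.

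This rests on an assumed number of vacancies, on reading *replaced* as refilling the vacated arm, and on someone having that knowledge. None of the three is established by the documents. It is an avoidable vulnerability affecting a few patients, not a demonstrated bias, and it alters no stated sample-size figure. It should be corrected before recruitment relies on the rule.

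**What to change.** Replace the closing sentence of the Randomization section with wording such as:

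> An assignment issued to a patient who is excluded before block placement is retired and not re-used. The next consented patient receives the next unused entry from a concealed list, generated in advance with spare entries and held by a person not involved in recruitment, the pre-block recheck or block placement. Enrolment continues until 20 patients have received a block.

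Under Power Analysis, change the target to about 10 per arm.

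This alone leaves one route open: someone who knows an issued arm could still let it influence the post-bypass recheck. To close it, release the assignment only after the patient has passed that recheck. Most replacements then become unnecessary, and the retirement rule covers the few patients lost between recheck and block. The timing sentence must be changed to match, and randomization at enrollment reconciled with randomization on the day of surgery. State also who prepares the solution and whether the block team is masked.

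Cost: a longer list, a short text change and no extra treated patients. With late release, the solution has to be prepared between the recheck and the block. The arms may end slightly unequal, raising the variance of the difference by 1.0% at 11 v 9 or 4.2% at 12 v 8.
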